Challenging the inflammatory response system: Are individuals with insomnia more reactive?

NCT02261597

Date: 02/26/2016

PART B

STUDY DESCRIPTION

TITLE OF PROTOCOL	Challenging the inflammatory response system: Are individuals with insomnia more reactive?
Principal Investigator	[name] PhD

B1. PURPOSE OF PROTOCOL

Primary objective: To investigate the inflammatory response to a physiological stress challenge in insomnia disorder. We expect that individuals with insomnia are more reactive, as manifested in a stronger response of inflammatory systems markers (interleukin [IL]-6, prostaglandin [PG]E2) to a physiological stress challenge (cold pressor test). In accordance, we expect a stronger autonomic (blood pressure, heart rate) and hypothalamus-pituitary-adrenal (HPA, cortisol) response to challenge in insomnia disorder compared to healthy controls.

Secondary objective 1: To investigate the ability to habituate to a repeated physiological stress challenge. We expect that the process of habituation is deteriorated in insomnia compared to healthy controls, as indicated by the lack of the inflammatory, autonomic, and HPA responses to decrease upon repeated exposure to the cold pressor test.

Secondary objective 2: To investigate whether the inflammatory response to challenge can be predicted by the sensitivity of immune cells to glucocorticoids. We expect that in insomnia, monocytes are less sensitive to the counter-inflammatory signal of cortisol, resulting in an exaggerated inflammatory response to a physiological stress challenge.

B2. SIGNIFICANCE AND BACKGROUND FOR THE STUDY

Sleep is critical for the regulation and maintenance of biological systems, and sleep deficiency, such as insomnia, has been shown to be associated with elevated risks for cardiovascular, metabolic, and mood disorders¹¹.

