In this light, the primary objective of this proposal will investigate whether the inflammatory, autonomic, and HPA systems are more reactive to a physiological stressful challenge in insomnia disorder compared to healthy controls.

Beside the hypothesized changes in the system's response reactivity in insomnia, the secondary objective 1 of this proposal will investigate the ability of system's responses to habituate to repeated stressful challenges. Habituation, or a decreased response following repeated exposures to a stressful challenge, is a key feature of the adaptive nature of many biological systems, and has been observed in response to a variety of psychological and physiological stressors and challenges in both humans and animals¹⁵. Considering that most individuals have to deal with stressful challenges on a daily basis, failure of systems to habituate to such daily challenges may elevate disease risk in the long term¹⁵. To test the degree of habituation, we will repeatedly administer the CPT and measure the inflammatory, autonomic, and HPA response magnitude after each challenge.

In summary, this proposal focuses on system's reactivity to challenge (primary objective) and the ability of systems to adapt to repeated challenges (secondary objective 1), rather than assessing basal systems activity only. Dysregulation of systems reactivity and habituation are likely to constitute processes that may serve as valuable predictors of disease risk in insomnia.

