Twenty sec after foot immersion into hot water bath (47 °C, the conditioning stimulus that is supposed to activate descending pain-inhibitory circuits), the participant rates the intensity of heat pulses (test stimulus, individually tailored to highest tolerable temperature) applied to the forearm.

inhibitory circuits and thereby decrease the perceived pain of the forearm test stimulus (see **Figure 2** for setup).

In total, four CPM trials will be performed: two trials using a hot water bath (47 °C) and two baseline trials without a water bath. For each hot water bath trial, the participant's foot will be first submerged in the water bath. After 20sec of immersion, the 10-pulse temporal summation sequence will be applied to the forearm and the participant will be prompted to rate the pain intensity of the 1st, 4th, 7th, and 10th stimulus using the VAS. There will be a two-minute rest period between all trials during which the thermode will be systematically moved from the distal to proximal sites along the C8-T1 innervated skin in order to avoid re-stimulation of the previously sensitized skin. For statistical analysis, ratings of the two 10-pulse sequences under the conditioning stimulus (hot water) will be averaged, and contrasted against ratings from the baseline (no-water) condition. A decrease in pain intensity ratings under the hot water condition compared to the no-water condition will be used as an index of the pain-inhibitory capacity.

B. Statistical Considerations

Sample Size Justification: For sufficient statistical power, we will need to have 20 participants with a diagnosis of insomnia disorder (based on DSM-V criteria), and 20 healthy control sleepers complete the study protocol (60% women, see power calculation below).

Power calculation

Power calculations were performed for the primary objective of this proposal. With respect to the proposed stronger **inflammatory response reactivity** in insomnia compared to healthy controls, power calculations were based on findings from Heffner et al.¹⁶, reporting a difference in the IL-6 response between poor and good sleepers to an acute challenge of 1.6 pg/ml (SD 1.71 pg/ml, estimated from graph). Thus, we need to study **20 participants in each group** to reach optimal power of 80% (unpaired t-test, alpha = 0.05).

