With respect to the proposed stronger **cortisol response reactivity** in insomnia compared to healthy controls, power calculations were based on findings from Goodin et al.¹⁴, reporting a difference in the cortisol response between poor and good sleepers to an acute challenge (CPT) of 10 units (area under the curve, SD 11 units, estimated from graph). Thus, 80% power will be reached with a sample size of N=20 per group

Statistics: Primary objective: Testing response reactivity to a physical challenge. The overall statistical analysis will be performed within the frame of mixed linear models. Primary and secondary outcome variables pertaining to the primary objective (see above) will constitute the independent variable, time (baseline, 1st CPT post-testing) and group (insomnia vs. healthy controls) will be entered as fixed factors, while subject number will serve as random factor. Simple contrasts will be performed between groups to identify differences at single time points.

Secondary objective 1: Testing response habituation to a repeated physical challenge. Data analysis will be similar as for the primary objective, but the time element will be presented by measures at baseline, 1st CPT post-testing, 2nd CPT post-testing, and 3rd CPT post-testing.

Secondary objective 2: GC sensitivity as a predictor of inflammatory response reactivity. Univariate analysis will be used to identify differences between insomnia and healthy controls in GC sensitivity at baseline. Regression analysis will be used to predict inflammatory response reactivity. Secondary objective 3: Actigraphy-based sleep characteristics as predictors of inflammatory, autonomic, and HPA response reactivity. Univariate analysis will be performed to identify differences in sleep variables (as mentioned under secondary outcome variables above). Regression analysis will

be used to predict response reactivity.

For all analysis, alpha will be set to 0.05.

C. Subject Selection

Human Subjects Involvement and Characteristics

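### The primary analysis does not name a test of a between-group difference in response: group × time is probably intended but not stated, and the stated model does not fit PGE2

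*Combined protocol and SAP*

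**What the plan says.** Section B1 expects people with insomnia to be more reactive, "as manifested in a stronger response of inflammatory systems markers (interleukin [IL]-6, prostaglandin [PG]E2) to a physiological stress challenge". Section B2 sums up the proposal as being about reactivity and adaptation "rather than assessing basal systems activity only".

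The power calculation in B3.B follows that aim. For IL-6 it relies on a published study "reporting a difference in the IL-6 response between poor and good sleepers to an acute challenge of 1.6 pg/ml", with SD 1.71 pg/ml, an unpaired t-test, alpha 0.05 and 80% power, giving 20 per group. For cortisol it uses a difference in response of 10 units ("area under the curve, SD 11 units, estimated from graph"), again with 20 per group.

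The Statistics text for the primary objective specifies a mixed linear model: "time (baseline, 1st CPT post-testing) and group (insomnia vs. healthy controls) will be entered as fixed factors", with subject as random factor. One comparison is named: "Simple contrasts will be performed between groups to identify differences at single time points". The outcomes "will constitute the independent variable", which is a slip, since they are the dependent variables. For secondary objective 1 (habituation), "Data analysis will be similar as for the primary objective", with four time levels instead of two.

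The primary analysis names no interaction, change score or baseline adjustment.

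**The concern.** The objective and the power calculation concern a difference in response. The stated comparison concerns a difference in level. A reader of the plan cannot tell which result decides the primary objective: a contrast at one time point, or an interaction that is not written down.

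The distinction matters here because the groups are matched on age and gender (B3.C) but not randomised, so their basal levels may differ. B2 is mixed on this. It cites reports of raised IL-6 in insomnia, but also says that basal IL-6 did not separate poor from good sleepers in the same study used for the IL-6 power calculation. If basal levels do differ, a post-CPT contrast can be significant with no difference in reactivity, which is the confusion the study sets out to avoid. Habituation inherits the gap.

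PGE2 is named alongside IL-6 in B1, but B3.A measures it in urine collected over the CPT series. It has no value specific to the first CPT, so the two-time-point model cannot be applied to it.

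**Working it through.** **The plan's own figures.** Two-sided unpaired t-test (the plan does not state sidedness), n = 20 per group, df = 38, critical t = 2.024, noncentrality = d × √(20/2).

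- IL-6: d = 1.6/1.71 = 0.936; noncentrality 2.959; power 82.2%. The smallest n for 80% is 19 per group, so the stated 20 is reproduced.
- Cortisol: d = 10/11 = 0.909; noncentrality 2.875; power 80.0%. Reproduced, for an area-under-the-curve comparison.

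**Link to group × time.** With two time points, complete data and a subject random effect, the group × time test is an unpaired t-test on change from baseline. If 1.71 is the SD of the response, as the text reads on its face, power for group × time is the same 82%.

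**What the level contrasts do when reactivity is equal.** The documents give neither a basal shift nor a baseline–post correlation ρ, so both are assumed. Let the insomnia group be shifted by b SD at both times, with equal SDs and an additive response.

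- Post-CPT contrast read alone: d = b. At b = 0.5, noncentrality = 0.5 × √10 = 1.581, and it is significant in 33.8% of trials. At b = 0 and 0.25 the figures are 5.0% and 12.0%.
- Group × time: the shift cancels in post minus baseline, so it is significant in 5% of trials for every b.
- Both contrasts read together: share of trials with baseline not significant and post-CPT significant (bivariate normal, 200,000 simulated trials per setting):

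| Assumed basal shift | ρ = 0.3 | ρ = 0.5 | ρ = 0.7 | ρ = 0.9 |
|---|---|---|---|---|
| 0 SD | 4.5% | 4.1% | 3.5% | 2.1% |
| 0.25 SD | 9.3% | 8.0% | 6.3% | 3.7% |
| 0.5 SD | 18.2% | 15.3% | 11.8% | 6.6% |

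**Scale.** The 5% for group × time depends on an additive response. Suppose instead a log-normal marker (assumed log SD 0.5) that exactly doubles in both groups, with a basal shift of 0.5 SD on the log scale. The interaction on the raw scale is then significant in roughly 10% to 22% of trials as ρ rises from 0.3 to 0.9. On the log scale it stays at 5%.

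**Sampling times in B3.A.**

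| Item | 1-Day CRC Visit | Procedures |
|---|---|---|
| Blood | Baseline assessment, including blood, ends at 12pm | Blood Sampling: draws run from 1pm to 7pm |
| Urine around the CPT series | 1pm to 6pm | PGE2: 3pm to 7pm |
| Post-CPT blood | 20 and 50 min after hand removal | The same two times |

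The Statistics text does not say which of the two post-CPT samples is the first-CPT value.

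**The case against.** The strongest reply is that the text already implies the missing term. In a model with additive time and group effects, the group difference is the same at every time point, so contrasts at single time points make sense only if group × time is in the model. The heading of that paragraph speaks of testing response reactivity, and the power calculation for the primary objective uses a t-test on a difference in response. This stands as evidence of intent. It does not make the interaction the deciding test, because the only comparison written into the analysis is still one of levels.

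A reader might infer that the plan tests a group main effect, which under the same 0.5 SD shift would be significant in 35–48% of trials (ρ 0.9 to 0.3), or that it reads the post-CPT contrast alone. The plan states neither rule. It refers to time points in the plural, so the pattern with both contrasts read is the closest to the text.

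A reader might also infer that no baseline can be defined because a 2pm sample, after the first CPT at 1pm, is called baseline. That sample is for glucocorticoid sensitivity only. The 1am start printed for the baseline period precedes the 10am line placement and is evidently a slip. The conflict that remains is baseline blood before noon against sampling from 1pm.

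Finally, the choice of change over covariate adjustment for PGE2, and of any particular habituation contrast, is partly preference. At a 0.5 SD shift, covariate adjustment leaves 19% to 6% false positives (ρ 0.3 to 0.9) against 5% for change, but that comparison assumes an equal additive shift at both times.

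**Conclusion.** The point holds as a specification gap that should be fixed before the data are analysed. No stated test answers the primary objective, and the stated model cannot be applied to PGE2. The interaction was probably meant.

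The size is conditional. At an assumed 0.5 SD basal shift, the misleading pattern occurs in 7–18% of trials and the post-CPT contrast alone is significant in 34%, against 5% for group × time with an additive response. At 0.25 SD the pattern is 4–9%. With no basal shift there is no excess. These are illustrations, not the trial's error rate.

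A reader might infer that the trial is too small for an interaction. The documents do not support that. If 1.71 were the SD of a single level, the SD of change would be 1.71 × √(2(1−ρ)), and power would fall to 68% at ρ = 0.3. But the text presents the figure alongside a difference in response, and on that reading power is 82%.

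**What to change.** Rewrite the primary analysis to state that:

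- the outcomes are the dependent variables;
- the fixed effects are group, time and group × time, with subject as random effect;
- for blood and autonomic outcomes, the test of reactivity is the group × time interaction, that is, the group difference in change from a named pre-CPT baseline sample to a named first-CPT post value (20 min, 50 min or their mean);
- the scale is fixed in advance, for example log-transformed IL-6 and cortisol if skewed;
- contrasts at single time points are follow-up only.

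For habituation, use the group × time test with one contrast fixed in advance.

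Analyse PGE2 separately, as the group difference in change in creatinine-adjusted level from the baseline urine already collected at the 1-Day CRC Visit to the CPT-series urine.

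In B3.A, reconcile baseline blood before noon with sampling from 1pm, and the two urine windows (1pm–6pm and 3pm–7pm).

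Cost: wording only for the blood and autonomic outcomes. If baseline urine is not already assayed for PGE2, up to 40 extra assays (one for each of 20 + 20 participants). The sample size is unchanged. The plan should say that the IL-6 power figure is on the raw scale and does not carry over directly to a log-scale analysis, and that the cortisol 80% applies to an area-under-the-curve comparison.

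### Group differences at the second and third cold pressor test carry the expected reactivity difference forward, so they cannot be read as failed habituation

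*Combined protocol and SAP*

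**What the plan says.** B1 sets out two separate hypotheses. The primary one concerns the size of the first response: "We expect that individuals with insomnia are more reactive, as manifested in a stronger response of inflammatory systems markers". Secondary objective 1 concerns what happens on repetition: habituation is expected to be impaired in insomnia, "as indicated by the lack of the inflammatory, autonomic, and HPA responses to decrease upon repeated exposure". B2 describes habituation in general terms as a response that becomes smaller with repeated exposure. Neither section says whether the decrease is counted in units or as a share of the first response.

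B3.B (Statistics) analyses the primary objective with a linear mixed model: time and group as fixed factors, subject as random factor, and simple contrasts between groups at single time points. For secondary objective 1 the analysis is to be similar, except that "the time element will be presented by measures at baseline, 1st CPT post-testing, 2nd CPT post-testing, and 3rd CPT post-testing". Neither paragraph names a group-by-time term, a contrast between the first and later CPTs, a transformation, a response ratio or an adjustment for the first response.

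The sample size rests on "a difference in the IL-6 response between poor and good sleepers to an acute challenge of 1.6 pg/ml", with SD 1.71 pg/ml. B3.B adds: "Power calculations were performed for the primary objective of this proposal". No calculation is given for habituation.

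**The concern.** If the primary hypothesis is right, the groups already differ after the first CPT. Unless that gap closes completely, they still differ after the second and third. A contrast between groups at one of those time points measures what is left of the reactivity difference plus any difference in habituation, and cannot separate the two.

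Followed as written, the plan could report impaired habituation in insomnia when both groups habituate equally, or when neither habituates at all. Secondary objective 1 would then repeat the primary result under another name.

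**Working it through.** **Inputs from B3.B.** Expected difference in IL-6 response 1.6 pg/ml, SD 1.71 pg/ml, 20 per group, "unpaired t-test, alpha = 0.05". Sidedness is not stated; two-sided is used because it reproduces the plan's sample size (one-sided gives 15 per group).

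**Plan's own figure.** n = 2 × (1.96 + 0.842)² × (1.71/1.6)² = 15.70 × 1.142 = 17.9, so 18 per group, or 19 with the t distribution. Power at 20 per group is 82.2%. For cortisol (10 units, SD 11), 15.70 × 1.21 = 19.0, or 20 with the t distribution, with power 80.0%. The stated 20 per group is reproduced.

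**Assumptions not in the documents.** Equal mean baselines; SD 1.71 at the third CPT as at the first; control first response c (0.8, 1.6 or 2.4 pg/ml); insomnia first response c + 1.6; fractional decline h from first to third CPT; correlation 0.5 to 0.7 between a person's first and third responses.

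**Contrast at the third CPT (the type the plan names).** If both groups decline by the same fraction, the difference is (1 − h) × 1.6, whatever c is.

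| Common decline h | Difference at CPT 3 (pg/ml) | Trials significant |
|---|---|---|
| 0 (neither group habituates) | 1.60 | 82% |
| 0.3 | 1.12 | 52% |
| 0.5 | 0.80 | 30% |
| 0.7 | 0.48 | 14% |

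In every row habituation is equal, yet insomnia appears not to have come down. The first row needs no choice between absolute and proportional habituation.

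**Contrast on the change from CPT 1 to CPT 3.** The difference in decline is h_I × (c + 1.6) − h_C × c.

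- Neither group habituates: 0, so the test rejects in its nominal 5%. This removes the worst case above.
- Both decline by 50%: 0.5 × 1.6 = 0.8 pg/ml, with insomnia declining by more units. The SD of the decline is 1.71 × √(2(1 − ρ)), that is 1.71 at ρ = 0.5 and 1.32 at ρ = 0.7, giving significance in 30% and 46% of trials.
- Controls 50%, insomnia 25%: 0.25 × (c + 1.6) − 0.5c = 0.4 − 0.25c, which is +0.2, 0 and −0.2 pg/ml for c = 0.8, 1.6 and 2.4.
- Controls 50%, insomnia none: the difference is −0.5c. Power is 11–16% at c = 0.8 and 30–46% at c = 1.6.

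A change contrast is therefore needed, but it still scales with the first response.

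**Retained fraction (CPT 3 response / CPT 1 response).** With controls at 0.50, equal habituation gives 0.50 in insomnia, half-strength gives 0.75 and none gives 1.00, whatever c is. Rejection rates come from 20,000 simulated trials per case, with bivariate normal responses, a delta-method test of the ratio of means and critical value 1.96. At c = 1.6 the test rejects in about 4% under equal habituation. Power, over ρ = 0.5 to 0.7:

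| c (pg/ml) | Half-strength in insomnia | None in insomnia |
|---|---|---|
| 0.8 | 4–5% | 18–19% |
| 1.6 | about 20% | 54–70% |
| 2.4 | 34–44% | 83–95% |

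At c = 0.8 the control group's first response is itself not significantly above zero in about 49% of trials.

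**The case against.** **The scale is not stated.** The plan says only that the analysis is similar, so absolute units are the default reading of a linear model sized in pg/ml, not a declared choice. That is fair. But the result when neither group habituates does not depend on a proportional definition, and silence leaves the choice open until the data are seen.

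**A group-by-time test may be intended.** None is named. If the four-level interaction were used, it would include the step from baseline to the first CPT. In a simulation with an assumed within-subject SD of 1.71/√2 and c = 1.6, it rejects in about 86% of trials when neither group habituates and about 72% under equal 50% habituation. It does not isolate habituation either.

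**The plan predicts no decrease in insomnia, not a partial one.** In that case the absolute decline and the retained fraction point the same way. This stands. The two diverge only under equal or partial habituation, which the analysis must still be able to tell apart from the hypothesis.

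**Stronger readings.** A reader might infer that the plan would make half-strength habituation invisible, would show equal habituation as better habituation in insomnia, or lacks power to detect absent habituation. The documents do not support these. All three belong to a CPT 1-to-CPT 3 decline contrast that the plan never names, and exact cancellation needs c = 1.6 pg/ml, which the documents neither give nor exclude. The contrast the plan does name is significant in 82% of trials for half-strength and 99% for absent habituation at c = 1.6. Its fault is lack of specificity, not of power.

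**Limits of a ratio.** Urinary PGE2 is collected over the CPT series, so no ratio by test can be formed. There is one baseline, and B3.A gives the interval between tests as 1.5 hours in the overview and 60 minutes under Procedures, with a blood draw at 50 minutes. Carry-over into later responses is possible, and any change or ratio measure inherits it. The two intervals must be reconciled.

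**Conclusion.** The concern holds in this form: under the plan's own expectation of a larger first response, single-time-point group contrasts at the second and third CPT cannot be read as evidence on habituation. At the plan's IL-6 figures, the third-CPT contrast is significant in about 82% of trials when neither group habituates and about 30% when both decline by 50%.

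These percentages assume equal baselines, SD 1.71 pg/ml at the third CPT and two-sided testing. Contrasts on raw marker levels with a larger SD would give lower percentages; the size of the carried-over difference would not change. The documents do not show that absolute units were chosen deliberately, nor that habituation must be defined proportionally.

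The primary objective and sample size are unaffected. The point should be settled before analysis, because it decides what secondary objective 1 can claim.

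**What to change.** In B3.B, Secondary objective 1, for markers measured after each CPT (IL-6, cortisol, autonomic measures):

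1. Define the response to each CPT as change from baseline, stating how the 20- and 50-minute samples enter for the blood markers.
2. Base the habituation conclusion on the change from the CPT 1 response to the CPT 2 and CPT 3 responses, compared between groups in the same mixed model (group × CPT number on baseline-corrected responses).
3. Report with it each group's retained fraction (mean CPT 3 response / mean CPT 1 response) and a confidence interval for the group difference, by delta method or participant bootstrap.
4. Keep single-time-point group contrasts as descriptive. Do not claim impaired habituation from them, or when the retained fraction is not higher in insomnia. Do not read a null change contrast as intact habituation.
5. Report the retained fraction as not estimable where a group's mean first response is not clearly above zero. State that urinary PGE2 is outside this analysis.

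This changes analysis wording only; no samples or participants are added. The downside is imprecision. With a control first response of 0.8 to 2.4 pg/ml and 50% habituation in controls (both assumed), the retained-fraction test has about 4–44% power for half-strength and 18–95% for absent habituation in insomnia. Item 5 would also leave many trials without an estimate at the low end. The gain is a result that can be interpreted, not a more sensitive one.
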